#### **Study Protocol**

#### Title:

Feasibility of assessing economic and sexual risk behaviors using text message surveys in African-American young adults experiencing homelessness and unemployment: a single-group study

#### Aim:

This study examined the feasibility of assessing sexual and economic behaviors using text message surveys in African-American young adults who were out-of-school and experiencing homelessness and unemployment. Specifically, this manuscript describes the process, challenges, and solutions with regard to text message survey responsiveness and utility. Implications for using text message surveys in future HIV behavioral intervention trials are also discussed.

#### Methods:

#### Design

A single-group cohort study was used to examine the feasibility of assessing economic and sexual risk behaviors using weekly text message surveys. Participants were invited to respond to a text message survey sent to their cell phone every Monday at 9:00 AM for 5 weeks.

## Setting

The study was conducted in Baltimore, MD. The majority (82%) of HIV diagnoses in Baltimore are among African-Americans, with young adults, aged 20 to 29, representing the highest proportion. Young adults in the city make up an increasing proportion of the homeless and unemployed. Youth experiencing homelessness are 6 to 12 times more likely to become infected with HIV than housed youth, with prevalence rates as high as 12%. HIV prevalence among African-Americans in Baltimore is 3.1%, over ten times the national HIV prevalence in the U.S. (0.3%) and exceeding the UNAIDS definition of a generalized epidemic (HIV prevalence > 1%).

### Recruitment & Enrollment

Potential participants were recruited on-site from two community-based organizations (CBO) providing emergency and supportive residential services to young adults in Baltimore, MD. A recruitment flyer was posted in the main building of both CBOs. Designated CBO staff introduced potential participants to the study team on scheduled visit days. Study eligibility was determined using a paper-based screening questionnaire that was administered by a trained research assistant. Individuals were eligible to participate if, at the time of enrollment, they were: African American, aged 18 to 24, living in Baltimore, experiencing homelessness within the last 12 months, unemployed or underemployed (≤ 10 hours per week), out-of-school, reporting one or more episodes of unprotected sex in the last 12 months, and having a cell phone that could send and receive text messages. Eligible participants were then introduced to the study and administered informed consent.

As part of the enrollment process, we invited participants to register their cell phone to the text message survey application. Participants sent a text message with the word "join" to the study phone number in order to register. Each person then received a brief orientation regarding the survey's content, timing, and payment incentive (\$20 in cash). In the presence of a trained research assistant, the participant also completed on his/her cell phone a mock, but identical version of the 14-question text message survey. This was done in order to confirm readability of the text message questions and their prompts and to clarify any points of confusion. Participants were also advised on how to opt out of the survey by sending a text with the word "leave" at any time. As a final orientation step, participants were advised on how to increase privacy during the study period, such as activating cell phone passwords, deleting all text message surveys, responding only to the study's phone number, and answering in a quiet and private space.

### Text Survey Design

We used *Textlt.in* to create, send, and receive text messages from participants. Textlt.in is an online service for building text messaging applications using a visual and interactive flow. The text message survey was powered by *Twillio*, a cloud communications platform, using a study-sponsored phone number. We then developed an online logic tree to order how survey questions would be texted to the participants. Figure 1 shows an excerpt of the branch logic used in the question tree. To facilitate responsiveness and data quality, the text messaging application included automated reminders and quality check prompts. Participants had 24 hours to complete each weekly text message survey. One automated text message reminder was sent to participants who did not initiate responding to the survey or to those who started but did not complete the survey within the first 24 hours. Reminder text messages included the name of the study, the payment incentive, and a reminder to respond to the survey within the next 24 hours. In addition, participants who responded with ineligible words or numbers outside of pre-set ranges received a text message query asking them to re-enter a valid response. All completed surveys generated one automatic text message that thanked the participant for his/her time.

#### Measures

Data were collected in August and September 2017. Participants received the same 14 questions as text messages each week regardless of their responses to the week's prior text message survey. Table 1 lists each question used in the survey. All questions were in English and referred to the last 7 days, equivalent to the prior week. Eligible responses were: yes/no or number of units (i.e., dollars, episodes, people). There were 7 economic questions relating to: involvement in any type of paid work; the amount of cash earned from a job; the amount of cash earned from one's own business; the amount of cash deposited into a savings account; the occurrence of loss of housing; the occurrence of requesting for cash to meet living expenses; and the amount of cash spent on any HIV preventive services or products. An additional 7 sexual behavioral questions inquired about the: number of sex partners; engagement in sex while high or drunk; frequency of condomless sex; utilization of other non-condom HIV preventive methods; frequency of sex exchange; discussion of HIV testing with sex partners; and receipt of HIV testing.

Our primary feasibility measures were: number of participants who responded to the survey in a given week; number of questions to which a participant responded in a given week; and number of hours from sending a survey to participants to receiving their response in a given week. We calculated the number, mean, and proportion of participants who responded to each question in each of the weekly surveys over the 5-week study period. A participant was categorized as responding to the question if s/he provided a valid response such as "yes/no", a numerical response, a free-form text, or a "skip" response in order to proceed to the next question. A participant was categorized as responding to the survey if s/he provided a valid response to at least one question of the 14-question survey. Non-responders were defined as enrolled participants who did not return a text message response to any of the text message surveys over the course of the study period. As part of the study's process evaluation, one discussion group with 5 responders was used to obtain feedback. Non-responders were also invited. The study team additionally documented in memo notes the implementation lessons learned.

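### A skip counts as responding to a question, so the questions-answered count and the per-question proportions measure engagement and can overstate how many items yielded behavioural data

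*Combined protocol and SAP*

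**What the plan says.** The Measures section names three primary feasibility measures: weekly responders, questions responded to per participant per week, and hours to response. It adds a per-question summary: "We calculated the number, mean, and proportion of participants who responded to each question in each of the weekly surveys".

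Two definitions drive these. A question is responded to if the reply is a yes/no, "a numerical response, a free-form text, or a 'skip' response in order to proceed to the next question". A participant responds to the survey if he or she "provided a valid response to at least one question of the 14-question survey". Earlier, the same section restricts eligible answers to yes/no or a number of units. Skips and free-form text are outside that list, yet both count as valid replies.

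The Text Survey Design section adds a data check: "participants who responded with ineligible words or numbers outside of pre-set ranges received a text message query". It also says "Figure 1 shows an excerpt of the branch logic used in the question tree", and the Measures section says "Table 1 lists each question used in the survey". Neither the figure nor the table is in the text available for this review, which is not a fault of the plan.

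The Statistical Analysis Plan calculates the feasibility measures as defined under Measures, then behaviour frequencies by specific response for each weekly question, and then a synthesis of lessons in five domains, one of which is data quality. The reply to every question in every week is stored.

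**The concern.** The Aim is the feasibility of assessing behaviours, and "this manuscript describes the process, challenges, and solutions with regard to text message survey responsiveness and utility". Responsiveness is a matter of engagement. Utility also depends on how many replies carry behavioural data, and no specified measure gives that. Because a skip earns the same credit as an answer, a participant can score 14 of 14 while leaving several items without content.

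Seven of the 14 items are about sexual behaviour, including condomless sex and sex exchange. If declined items were concentrated there, the response proportions alone would not show it. A future HIV intervention trial that uses these results to plan the completeness of its outcome data needs the usable-answer rate. No hypothesis test or progression threshold depends on the point. What is at stake is the conclusion about data yield.

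**Working it through.** The plan states no skip rate, response target or sample size, so there is no figure of its own to reproduce. The check follows the definitions through each measure. The documents supply the 14 questions (7 economic, 7 sexual) and the 5 weeks. All other values are assumptions, marked as such.

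**1. Per-question proportion.** Let r be the proportion counted as responding, and d the share of those replies that are uninformative skips. The usable proportion is r(1 − d) and the overstatement is r·d. With r = 80% (assumed):

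| d (assumed) | usable, r(1 − d) | overstatement, r·d |
|---|---|---|
| 0% | 80% | 0 points |
| 5% | 76% | 4 points |
| 10% | 72% | 8 points |
| 25% | 60% | 20 points |

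**2. Questions-answered count.** Suppose (assumed pattern) that a participant replies to everything but skips the four sexual items that seem to presuppose a partner: sex while high or drunk, condomless sex, sex exchange, and discussing testing with partners. The score is 14 in every case.
- All four declined: 14 − 4 = 10 informative items (10/14 = 71%); sexual items 7 − 4 = 3 of 7 (43%).
- All four not applicable after an answer of zero partners: 14 of 14 informative, and 7 of 7 sexual items.
- Over 5 weeks the score is 14 × 5 = 70, of which 50 to 70 are informative; for the sexual items, 15 to 35 of 35.

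The score cannot tell these cases apart.

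**3. Weekly responder count.** This is overstated only for a participant with no usable answer at all that week. If skips were independent (assumed; clustering by person would raise the figure), the chance that all m replies are skips is d^m. At d = 25%:
- m = 1: 25%
- m = 2: 0.25² = 6.3%
- m = 14: 0.25^14, about 4 × 10⁻⁹

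The effect is confined to people who send very few replies.

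**4. Hours to response.** Nothing in the documents shows that counting skips affects this measure.

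**5. Behaviour frequencies.** Take 100 participants (assumed), r = 80% and d = 25%. That gives 80 replies, of which 20 are skips and 60 are answers. Let half the answers be yes, so 30.
- If all 20 skips are declined, the frequency among those who gave information is 30/60 = 50%. Keeping the skips in the denominator dilutes it to 30/80 = 37.5%.
- If all 20 skips are not applicable because of zero partners, they are informative noes. Then 30/80 = 37.5% is the right figure, and dropping them would inflate it to 50%.

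At d = 5% and 10%, the diluted figure is 0.50 × 0.95 = 47.5% and 0.50 × 0.90 = 45.0%. No single denominator suits both kinds of skip, so the rule has to separate them.

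**The case against.** The best defence has four parts.

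- **The rule is openly stated and is a fair measure of engagement.** This stands. The any-reply measures should be kept.
- **The plan looks beyond reply counts.** It has re-entry prompts, a data-quality domain and frequencies by specific response. These lessen the gap. Tabulating by response value might show skips, and subtracting behavioural answers from the number responding would give skips plus uncoded text. But the prompts limit invalid text and do not touch skips, which are valid by definition. The data-quality domain is a qualitative synthesis. None of the three specifies a skip count or usable-answer rate.
- **A skip may be mere navigation, a refusal or not applicable, and the size rests on assumptions.** This also stands. The range above includes no loss at all.
- **The study is descriptive and the raw replies are kept.** This is true, and it makes the gap cheap to repair.

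A reader might infer more than this: that all the response measures are materially inflated, or that participants withheld sexual information. The documents support neither. The weekly responder count is barely affected, hours to response is not shown to be affected, and there are no skip data by item. A reader might also treat the unstated base of the proportions as an error in its own right; alone, it is only a missing detail.

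**Conclusion.** The point holds in limited form. By the plan's own definition, the questions-answered count and the per-question proportions credit skips, and free-form text outside the list of eligible answers, as responses. They show engagement and can overstate the yield of behavioural data. The weekly responder count is exposed only among people who send few replies.

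The true size is unknown and may be zero. Under the assumed values above, the per-question overstatement is 4 to 20 percentage points, and the four-item pattern gives 10 to 14 informative items behind a score of 14. These figures show how sensitive the measures are; they do not estimate what happened. The wording of the rule is certain. Its consequence depends on how often participants skipped and on what a skip meant for each item.

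It is worth correcting, because a primary measure and the main conclusion about assessing behaviours rest on it, and the stored responses allow it.

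**What to change.** - Keep the any-reply measures and label them engagement.
- From the stored responses, report for each question and week the number of usable answers (yes/no, in-range number, or text that can be coded to one of these) and the number of skips. Give subtotals for the 7 economic and 7 sexual items.
- Base statements about the feasibility of assessing behaviours on the usable-answer rate, and state its denominator.
- In the behaviour frequencies, exclude declined skips from the denominator. Count a skip that an earlier answer makes not applicable, such as one following zero partners, as an informative no or zero. The study team can set this rule item by item from Table 1 and Figure 1.

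The cost is a small recode and a short coding rule for free-form text and not-applicable skips. No new data are needed. The headline figures may look less favourable.

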### Statistical Analysis Plan

To analyze the results of the text message survey, we first created a database in Excel that included: a cell phone number for each participant, a participant unique study ID, demographic data relating to participant age, gender, education level, years living in Baltimore, number of hours worked per week, number of children living in and out of the household, the date and time of study enrollment, the date and time of all outgoing and/or incoming messages, and the numerical, textual, or free-from text message response to each of the 14 text message questions each week. Secondly, we calculated the study's primary feasibility measures as listed above. As a third step, we calculated

the frequencies of sexual and economic behaviors per the specific responses for each weekly question. Lastly, lessons learned from the study's process evaluation were synthesized over five implementation domains: acceptability, enrollment and registration, responsiveness, data quality, and data access.

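### Does the plan need a comparison of participants who replied with those who did not?

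*Combined protocol and SAP*

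**What the plan says.** The Measures section defines two levels of reply. At study level, "Non-responders were defined as enrolled participants who did not return a text message response to any of the text message surveys" during the study period. At weekly level, a participant counts as "responding to the survey if s/he provided a valid response to at least one question of the 14-question survey".

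The Statistical Analysis Plan lists four steps: build one database, calculate the primary feasibility measures, calculate "the frequencies of sexual and economic behaviors per the specific responses for each weekly question", and synthesise lessons from the process evaluation under five domains, one of which is responsiveness. The database includes "demographic data relating to participant age, gender, education level, years living in Baltimore, number of hours worked per week", children in and out of the household, enrolment time, all message times and each weekly answer.

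On the qualitative side, Measures says that "one discussion group with 5 responders was used to obtain feedback", that non-responders were invited too, and that the study team kept memo notes on implementation.

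**The concern.** The plan names a group, holds data on it, and then does nothing quantitative with it. The listed demographics enter no stated analysis step, and non-responders reappear only as invitees to the discussion group.

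The Aim covers survey responsiveness and utility, with implications for later HIV behavioural intervention trials. A team planning such a trial would want to know who replies as well as how many. Selective reply is plausible here: two of the weekly items ask about losing housing and asking for cash, and such circumstances could affect access to a phone or interest in the $20 incentive. If those who replied differ from those who did not, the behaviour frequencies describe the repliers and could be misread as describing everyone enrolled.

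A smaller point adds to this. A valid response may be "a numerical response, a free-form text, or a 'skip' response in order to proceed to the next question", so a reader cannot tell whether skips belong in the denominator of the behaviour frequencies.

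**Working it through.** The documents give no sample size, expected reply rate or behaviour frequency, so there is no figure to reproduce. The check has four parts.

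**1. What each step depends on.**
- Feasibility measures (participants responding, questions answered, hours to reply): reply behaviour is itself the outcome. Selective reply does not bias a count of replies.
- Behaviour frequencies: calculated from responses received. They are correct for those who answered. Selectivity matters only if they are read as applying to all enrolled.
- Process synthesis: covers responsiveness qualitatively, using the discussion group and memo notes. It is not a comparison of groups.

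**2. How far a frequency could be off for all enrolled.** Let r be the share answering, pA the frequency among answerers and pN that among non-answerers. The frequency in all enrolled is r × pA + (1 − r) × pN, so

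shift = pA − [r × pA + (1 − r) × pN] = (1 − r) × (pA − pN).

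All inputs below are assumed.

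| Share answering r | Shift if pA − pN = 10 points | Shift if pA − pN = 20 points |
|---|---|---|
| 80% | 0.20 × 10 = 2 points | 0.20 × 20 = 4 points |
| 60% | 0.40 × 10 = 4 points | 0.40 × 20 = 8 points |
| 50% | 0.50 × 10 = 5 points | 0.50 × 20 = 10 points |

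With no difference the shift is zero. The identity holds for any survey with non-response and says nothing specific about this one.

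**3. Whether a table by reply status would supply the missing quantity.** The unknown is pN.
- People who never replied have no weekly answers, and the database lists no baseline sexual-behaviour variable.
- No baseline housing measure is listed, and everyone entered as "experiencing homelessness within the last 12 months, unemployed or underemployed". Hours worked were capped at 10 a week at entry, so they give little contrast.
- What remains is age, gender, education, years in Baltimore and children. These describe who replied. They do not estimate pN, so they cannot measure, bound or correct the shifts in part 2.
- The never-replied column may be very small. Assuming 20 to 60 enrolled and 10% to 20% never replying, it holds 20 × 0.10 = 2 to 60 × 0.20 = 12 people. The exact 95% interval for an observed half is 0.07 to 0.93 with 4 people (2 of 4) and 0.21 to 0.79 with 12 (6 of 12).

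**4. Whether the weekly answers could be used instead.** Five surveys give 5 − 1 = 4 consecutive-week pairs per participant, so next-week non-response could be tabulated by the previous week's housing-loss and cash-request answers. That leaves out people who never replied. Also, because each question "referred to the last 7 days, equivalent to the prior week", a loss of housing in the week just before a missed survey is not recorded by that survey. It would be a new exploratory analysis that misses the group at issue.

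**The case for a change.** The best case for a change is that the table is nearly free. The data are already held, no test is needed, and a feasibility report on text surveys is more useful if it says who replied. Grouping by number of weeks responded (0, 1–4, 5) would also place partial responders, whom the study-level definition leaves out. It would bring out an edge case too: someone who sent only invalid replies did return a text, so is not a non-responder, yet never responded to a survey. The process evaluation does not replace such a table, since the discussion group is described as 5 responders.

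Most of this stands as a description. No quantitative comparison is planned, the responsiveness domain and memo notes do not amount to one, and the table would be reasonable to report. What does not stand is the step from there to a defect. It is too strong to say the study cannot examine who replied: the data are in hand, and a short plan's silence does not prevent an analyst from tabulating them. Nor does the Aim promise predictors of response or behaviour estimates for all enrolled.

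The skip question is a missing reporting detail. The natural reading of the third step is answers actually given, and the rule counting a skip as a response is stated for the feasibility counts. Printing the numerator and denominator for each item settles it.

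**Conclusion.** The omission is real, but the plan can stand. Followed exactly as written, it gives sound primary feasibility measures and sound descriptive frequencies for those who answered. Any distortion in reading those frequencies as applying to all enrolled has unknown size and direction. The 2 to 5 points for a 10-point difference rest wholly on assumed reply rates of 80% to 50%, and the table the concern points to would not reduce that uncertainty.

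Tabulating baseline characteristics by weeks responded would be good descriptive practice. With data collected in August and September 2017 it would be post hoc and should be labelled so. It is optional, would say who replied, and would not reveal or remove bias in the behaviour frequencies. This conclusion assumes the frequencies are presented as describing those who answered, which is the plain reading of the plan. It would weaken if they were offered as estimates for everyone enrolled.
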